2.7.1.3 Other secondary efficacy endpoints

Time to treatment failure (TTF) is defined for patients in FAS as the time from date of randomization to an event of treatment failure. The events that constitute ‘treatment failure’ are described in the Appendix. They are based on the ELN criteria [[Baccarani et al. 2013](#)] defining failure of a second line treatment adapted to include discontinuation of randomized treatment as an event.

TTF (in months) is calculated as: (date of treatment failure or censoring date (see [Section 2.7.3](#)) - date of randomization + 1)/30.4375.

Progression-Free-Survival (PFS) is defined for patients in FAS as the time from the date of randomization to the earliest occurrence of documented disease progression to AP/BC or the date of death from any cause (including progressions and deaths observed during the survival follow-up period).

PFS (in months) is calculated as: (date of disease progression/death or censoring date (see [Section 2.7.3](#)) - date of randomization + 1)/30.4375.

Overall survival (OS) is defined for patients in FAS as the time from the date of randomization to the date of death (including the survival follow-up period).

OS (in months) is calculated as: (date of death or censoring date (see [Section 2.7.3](#)) - date of randomization + 1)/30.4375, regardless whether the patient switched from bosutinib to asciminib.

2.7.2 Statistical hypothesis, model, and method of analysis

No confirmatory statistical testing of non-key secondary efficacy endpoints will be performed, however, nominal p-values will be presented for exploratory purposes (as specified in protocol Section 10.5.2).

MMR rates at and by time points

The FAS will be used for these endpoints. For each time point the MMR rate and the associated 95% confidence interval based on the Pearson-Clopper method will be presented by treatment group. The descriptive p-value obtained via CMH chi-square tests stratified by the randomization strata, i.e. MCyR vs no MCyR at screening, will be presented. A 95% confidence

interval for the difference in each MMR rate between treatment groups will be provided using the Wald method. The Mantel-Haenszel estimate of the common risk difference and the corresponding 95% confidence interval will also be provided.

A post-hoc analysis of the MMR rate will be performed using the number of subjects with adequate follow-up as the denominator. Subjects will be included in the analysis at a timepoint whenever their time between the date of randomization and the cut-off date is equal or above this timepoint, regardless of whether they discontinued before.

The cumulative incidence of MMR by treatment group will be graphically displayed by an increasing step function. Each curve will increase each time (after randomization) at which a new responder is observed and thus will increase up to the best observed response rate (e.g. up to 50% if half of the patients in the analysis population are able to achieve MMR).

Molecular response at and by time points

Frequency and percentage of all molecular response categories (defined in [Appendix](#)) by treatment arm using FAS will be presented for each time point.

For the by-time-points summary, the within-patient best molecular response category up to the specific time points is used to calculate the frequency and percentage.

Time to MMR

The MMR Responder Set will be used. Descriptive statistics (minimum, maximum, median, quartiles, mean, sd) of time to MMR will be provided for the two treatment groups separately.

The FAS will be also used to perform similar Time-to-Event analyses as described below for duration of MMR.

A post-hoc analysis of time to MMR will also be performed considering discontinuation from treatment due to any reason, without prior achievement of MMR as a competing risk.

Time to MMR will be censored at the last molecular assessment (PCR) date on treatment prior to or at the cut-off date, if no events/competing risk occurred before or at the cut-off date or the EOT.

The estimated cumulative incidence rates and 95% confidence intervals at 12, 24, 48, 72 and 96 weeks will be presented for each treatment group. The cumulative incidence curve will be plotted.

Duration of MMR

The MMR Responder Set will be used. The survival distribution of duration of MMR will be estimated using the Kaplan-Meier method, and Kaplan-Meier curves, medians and 95% confidence intervals [[Brookmeyer and Crowley 1982](#)] of the medians, along with the proportion of patients who are still in MMR at 24, 48, 72 and 96 weeks and the associated 95% confidence intervals, will be presented for each treatment group.

CCyR rates at and by time points

The CCyR Analysis Set will be used for these endpoints.

For each time point the CCyR rate and the associated 95% confidence interval based on the Pearson-Clopper method will be presented by treatment group. The descriptive p-value obtained via CMH chi-square tests stratified by the randomization strata, i.e. MCyR vs no MCyR at screening, will be presented. A 95% confidence interval for the difference in each CCyR rate between treatment groups will be provided using the Wald method. The Mantel-Haenszel estimate of the common risk difference and the corresponding 95% confidence interval will also be provided.

The cumulative incidence of CCyR by treatment group will be graphically displayed by an increasing step function. Each curve will increase each time (after randomization) at which a new responder is observed and thus will increase up to the best observed response rate (e.g. up to 50% if half of the patients in the analysis population are able to achieve CCyR).

Cytogenetic response at and by time points

Frequency and percentage of all cytogenetic response categories (defined in [Section 2.7.1.2](#)) by treatment arm using FAS will be presented for each time point. A shift table comparing baseline and best post-baseline cytogenetic response categories by treatment will also be presented. All assessments of cytogenetic response categories will also be listed by treatment arm.

For the by-time-points summary, the within-patient best cytogenetic response category up to the specific time points is used to calculate the frequency and percentage.

Assessments of bone marrow aspirate at different time points will also be summarized.

Time to CCyR

The CCyR Responder Set will be used. Descriptive statistics (minimum, maximum, median, quartiles, mean, sd) of time to CCyR will be provided for the two treatment groups separately.

The CCyR analysis set will be also used to perform similar Time-to-Event analyses as described below for duration of CCyR.

Duration of CCyR

The CCyR Responder Set will be used. The survival distribution of duration of CCyR will be estimated using the Kaplan-Meier method, and Kaplan-Meier curves, medians and 95% confidence intervals [[Brookmeyer and Crowley 1982](#)] of the medians, along with the proportion of patients who are still in CCyR at 24, 48, 72 and 96 weeks and the associated 95% confidence intervals, will be presented for each treatment group.

TTF, PFS and OS

For each endpoint the survival distribution will be estimated using the Kaplan-Meier method, and Kaplan-Meier curves, medians and 95% confidence intervals [[Brookmeyer and Crowley 1982](#)] of the medians, along with the proportion of patients who have not experienced the respective events at 1, 3 and 5 years and the associated 95% confidence intervals, will be presented for each treatment group. The hazard ratio between the two treatments will be calculated, along with its 95% confidence interval, using a stratified Cox model. The descriptive p-value obtained using a stratified log-rank test will be also presented. The stratification will be

based on the randomization stratification factor, i.e. cytogenetic response status (MCyR vs no MCyR) at screening.

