 - Concomitant use with CYP3A4/5 inhibitors/inducers: further clarifications on necessary actions.
- Table 7-1 Visit evaluation schedule:
 - Exploratory BCR-ABL1 mutation analysis (Sanger Sequencing) for patients with mutations at Week 1 Day 1: rephrased to indicate that this assessment will be performed without any dedicated blood collection.

- [REDACTED]
- Removal of PGIC questionnaire at screening: the question should only be completed for patients on treatment.
- Week 6, 10 and 14: physical examination and extramedullary involvement to be performed only if new or ongoing adverse event since last visit. Chemistry and coagulation testings removed.
- Section 7.1.2 Screening, section 7.2.1.2 Bone marrow analysis and cytogenetics and Table 7-1 Visit evaluation schedule: timeframe for performing bone marrow aspirate and biopsy changed from 42 to 56 days. Historical bone marrow assessments performed before main informed consent form signature allowed if within 56 days of Week 1 Day 1.
- Section 7.1.2.2 Information to be collected on screening failures: correction of screening failure definition.
- Section 7.1.4 Treatment period: treatment failure added as a reason for stopping study treatment.
- Section 7.1.5 Visit windows: correction of the start of visit scheduled every two weeks.
- Section 7.1.6 Discontinuation of study treatment:
 - Has been made mandatory in case of pregnancy.
 - Confirmed loss of MMR in 2 consecutive tests rephrased for consistency with the efficacy assessments.
 - Ineligibility of patient due to detection of T315I or V299L mutations at any time has been added under the section describing the cases when a patient MUST be discontinued to remove any ambiguity.
- Section 7.1.7 Withdrawal of consent and Glossary of terms: these sections were added/updated to incorporate and reflect the European Economic Area (EEA) General Data Protection Regulation (GDPR) requirements.
- Section 7.2.1.1 Molecular response: definition of loss of MMR rephrased and harmonization of time points for BCR-ABL1 gene mutation analysis.
- Table 7.2 Blood samples (efficacy primary endpoint): updated to reflect:
 - [REDACTED]
 - Exploratory BCR-ABL1 mutation analysis (Sanger Sequencing) for patients with mutations at Week 1 Day 1 will be performed without any dedicated blood collection.

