Safety summaries (tables, figures) on the Safety set (respectively on the Switch Analysis Set) include only data from the on-treatment (resp. on-switched treatment) period with the exception of baseline data which will also be summarized where appropriate (e.g. change from baseline summaries). In particular, summary tables for adverse events (AEs) will summarize only on-treatment (resp. on-switched treatment) events, with a start date during the on-treatment (resp. on-switched treatment) period (**treatment-emergent** AEs) (resp. switched-treatment-emergent AEs). In addition, a separate summary for death including on-treatment and post-treatment deaths will be provided.

However, all safety data (including those from the pre-treatment, post-treatment and post-switched treatment period) will be listed and flagged as appropriate.

Efficacy summaries on the FAS (apart from OS and PFS) include data from baseline up to either the last assessment on or before the EoT visit or before or on treatment failure, whichever is the earliest.

Efficacy summaries on the Switch Analysis Set include data from baseline_switch up to the last assessment on or before the S-EoT visit or before or on treatment failure during the switched treatment period, whichever is the earliest.

The efficacy assessments collected post-treatment failure, post-EoT or post S-EoT visit are not included in any efficacy analyses (except for OS and PFS analyses). However, they will be listed and flagged as appropriate.

Windows for multiple assessments

Data such as molecular response, cytogenetic response collected over time (including unscheduled visits) will be summarized by scheduled time point. As patients do not always adhere to the visit schedule, visits will be remapped according to visit windows defined in Tables 2-1 to Table 2-4 of this document to enable by-visit analysis. Only those protocol-defined visits will have the visit window defined. Each assessment (including the end of treatment assessment), either scheduled or unscheduled, will have a mapped visit assigned, as long as study day is available, according to the defined visit window up to the date with data included.

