5.4.4 Treatment Failure

The following events will constitute 'treatment failure', and are based on the ELN criteria ([Baccarani et al 2013](#)) defining failure of a second line treatment adapted to include discontinuation of randomized treatment as an event:

- No CHR or > 95% Ph+ metaphases at three months after initiation of therapy or thereafter
- BCR-ABL1 ratio > 10% IS and/or > 65% Ph+ metaphases at six months after initiation of therapy or thereafter
- BCR-ABL1 ratio > 10% IS and/or > 35% Ph+ metaphases at 12 months after initiation of therapy or thereafter
- Loss of CHR, CCyR or PCyR at any time after initiation of therapy
- Detection of new BCR-ABL1 mutations which potentially cause resistance to study treatment (T315I and V299L), at any time after initiation of therapy
- Confirmed loss of MMR in 2 consecutive tests
- New clonal chromosome abnormalities in Ph+ cells: CCA/Ph+: at any time after initiation of therapy

- Discontinuation from randomized treatment for any reason* (Note that Reason for treatment discontinuation="completed" doesn't indicate a premature treatment discontinuation)

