5.5 Derivation of response rates and categories

5.5.1 Response rate at a specific time point

The molecular and cytogenetic response evaluations will be summarized by the following mutually exclusive categories which are based on the respective assessment within the time window:

- **Response categories** (sections 5.4.1 and 5.4.2): Patients with an available assessment at that time point (+/- time window) indicating any of the response categories.
- **No response:** Patients with assessment at that time point (+/- time window) indicating 'no response'
- **Missing:** Patients without an evaluable response assessment at that time point (+/- time window). This category is then further split into patients who are ongoing without treatment failure at the beginning of the relevant time window, patients who are ongoing with treatment failure at the beginning of the relevant time window, patients who discontinued due to lack of efficacy, disease progression (PD) or death and patients who discontinued due to other reasons.

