The cumulative incidence proportion (CIP) will be estimated using SAS procedure LIFETEST or PHREG with EVENTCODE=Code for event of interest (e.g. MMR) as option in the MODEL statement, whereas code=0 for censored subjects and any other code (e.g. code=2) for subjects who dropped out due to a competing risk. The estimated CIP at the defined time points will be presented with 95% CI together with number of subjects with events, number of subjects with competing risks, and number of subjects censored.

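### The post-hoc competing-risk analysis of time to MMR does not count on-drug treatment failure as a competing event, so cumulative MMR is overstated if those patients are censored at their last admissible PCR

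*Combined protocol and SAP*

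**What the plan says.** All references are to the SAP as amended by addendum 1.0, unless stated.

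- **Competing event.** Section 2.7.2 (Time to MMR) plans a post-hoc analysis "considering discontinuation from treatment due to any reason, without prior achievement of MMR as a competing risk". Section 5.6.3 codes 0 for censored patients and "any other code (e.g. code=2) for subjects who dropped out due to a competing risk".
- **Censoring.** Section 2.7.2 continues: "Time to MMR will be censored at the last molecular assessment (PCR) date on treatment prior to or at the cut-off date", and this applies "if no events/competing risk occurred before or at the cut-off date or the EOT". Cumulative incidence is to be reported at weeks 12, 24, 48, 72 and 96.
- **Admissible data.** Section 2.1.1 ends FAS efficacy data at the EoT visit or at treatment failure, whichever comes first. It adds: "The efficacy assessments collected post-treatment failure, post-EoT or post S-EoT visit are not included in any efficacy analyses", with OS and PFS as the only exceptions.
- **Failure without stopping drug.** Section 5.4.4 lists failure criteria that a patient can meet while still taking the drug, for example "BCR-ABL1 ratio > 10% IS and/or > 65% Ph+ metaphases at six months after initiation of therapy or thereafter". Section 5.5.1 provides a category for "patients who are ongoing with treatment failure at the beginning of the relevant time window".
- **Primary estimand.** Sections 2.5 and 2.5.1 treat discontinuation and meeting a failure criterion as two separate intercurrent events, and both count as non-response.

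**The concern.** A competing event is one after which the event of interest can no longer be observed. Under section 2.1.1, treatment failure without prior MMR is such an event, because no later PCR may count. The post-hoc analysis carries over only one of the estimand's two non-response events, namely discontinuation. A patient who has failed but is still on drug is therefore handled as censored, that is, as someone who could still respond with the same probability as those remaining at risk. These patients were removed because they were doing badly, so the censoring is informative and pushes the MMR curve up.

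The SAP accepts the principle elsewhere. In the Kaplan-Meier analysis of time to MMR (section 2.7.3), patients who stop for progression or death before responding have their censoring time moved to the longest follow-up in the arm, on the ground that response is out of reach.

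At stake is the accuracy of a descriptive curve. Section 2.7.2 also plans a step-function cumulative incidence of MMR that involves no such censoring, so the report could show two cumulative-incidence curves that disagree partly for this reason.

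**Working it through.** **Step 1: who is affected.** Going through section 5.4.4 for patients without prior MMR:

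- Loss of CHR and loss of CCyR count only if they led to discontinuation, or through progression to AP/BC or CML-related death on treatment (sections 5.4.2 and 5.4.3). The discontinuation route is already a competing event.
- T315I or V299L: the protocol Amendment 2 change log puts detection at any time among the cases for mandatory discontinuation. Already competing.
- Confirmed loss of MMR presupposes an MMR, so it is irrelevant here.
- What remains is the three-, six- and twelve-month milestones, loss of PCyR, and new clonal abnormalities in Ph+ cells. Of these patients, only those still on drug at cut-off are censored.

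**Step 2: what each coding does.** The cumulative incidence is

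F(t) = sum over u ≤ t of S(u−) × d(u)/n(u),

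with d(u) first MMRs, n(u) patients at risk, and S(u−) the probability of neither MMR nor a competing event before u. With N patients all followed past t:

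- Failure coded as competing: n and S fall together, S(u−) = n(u)/N, and each increment is d(u)/N.
- Censored at the last PCR actually taken: the failed patient stays in n and adds no MMR. S(u−) is still n(u)/N and each increment is again d(u)/N. Same answer.
- Censored at or before failure: n falls but S does not, so each later increment exceeds d(u)/N.

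**Step 3: limiting case by hand.** If a fraction f of the arm fails on drug before any MMR occurs, and true cumulative MMR is M, censoring at failure gives M/(1 − f). For f = 5, 10 and 20% this is:

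- M = 30%: 30/0.95 = 31.6; 30/0.90 = 33.3; 30/0.80 = 37.5
- M = 50%: 50/0.95 = 52.6; 50/0.90 = 55.6; 50/0.80 = 62.5

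**Step 4: simulation with staggered failures.** The SAP has no figure for this analysis to reproduce. The values 30% and 50% are borrowed from section 3.2, where they are bosutinib and asciminib rates at week 96; here they serve only as scenario values for cumulative MMR. Assumed, because the documents do not say: failures at weeks 12–48, another 20% discontinuing by week 96, accrual of about 100 weeks, cut-off at about LPFT + 96 weeks. Week-96 cumulative MMR (%), all failures staying on drug:

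| Failing | 30% scenario: censored at failure | Competing | Excess | 50% scenario: censored at failure | Competing | Excess |
|---|---|---|---|---|---|---|
| 5% | 31.4 | 30.1 | 1.3 | 52.0 | 49.9 | 2.1 |
| 10% | 32.7 | 30.0 | 2.7 | 54.4 | 49.9 | 4.5 |
| 20% | 35.9 | 30.0 | 5.9 | 60.7 | 50.5 | 10.2 |

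The censored figures lie a little below the limiting case, as they should when some MMRs precede failure. With fewer failures staying on drug, the week-96 excess over 5–20% failing is:

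| Share staying on drug | 30% scenario | 50% scenario |
|---|---|---|
| Half | 0.7–2.7 | 1.0–4.5 |
| 20% | 0.2–1.0 | 0.4–1.7 |
| None | 0 | 0 |

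At week 24 the excess is at most 0.7 points. Censoring at the last PCR actually taken gave the same result as the competing coding in every scenario at this cut-off.

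**The case against.** **The censoring rule can be read literally.** The rule specific to this analysis refers to the last PCR on treatment up to cut-off and says nothing of failure. Read that way, the excess is zero. This stands to the extent that the overstatement is conditional: a reader might infer that cumulative MMR is overstated as the plan is written, and the documents do not establish that. But the literal reading sets the censoring date from assessments that section 2.1.1 shuts out of every efficacy analysis except OS and PFS. Censoring at or before failure fits the SAP better. Two programmers could reasonably produce different curves.

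**The group may be small.** This stands. Step 1 narrows the criteria, failed patients who stop before cut-off are already competing events, and the Amendment 2 change log records "treatment failure added as a reason for stopping study treatment". Section 5.5.1 shows that on-drug failures are foreseen, not how many there are.

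**A reader might infer that the asciminib curve, and so the gap between arms, is inflated.** Only bosutinib failures have an in-study switch, which would turn them into competing events, while asciminib failures have none. The documents do not support the conclusion. Switching is an option, not a rule; the change-log entry on stopping names no arm; the current protocol text on discontinuation is not in the part supplied; and bosutinib may have more failures to begin with.

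**The stakes are limited.** This also stands. The analysis is labelled post-hoc, was added after database lock, and has no test attached. The cumulative MMR-by-visit rates on the FAS and the step-function curve do not use this censoring and allow a cross-check.

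**Conclusion.** The point holds in conditional form. Sections 2.7.2 and 5.6.3 make discontinuation the only competing event, while section 2.1.1 makes MMR uncountable after failure whether or not drug is stopped. If on-drug failures without prior MMR are censored at their last admissible PCR, cumulative MMR is biased upwards, mainly at weeks 48 to 96. If they are censored at the last PCR actually taken, there is no excess, but the analysis then conflicts with section 2.1.1. Either way the text needs reconciling.

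The size depends on two quantities that the SAP does not give: the share of an arm that fails without MMR and the share of those still on drug at cut-off. The ranges in the working are illustrations over assumed values, not estimates for this trial. The effect on the between-arm difference is undetermined. The primary and key secondary tests are unaffected.

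The wording reviewed is that of addendum 1.0. A further change log follows it in the file without its body, so I cannot tell whether the wording was kept.

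**What to change.** In sections 2.7.2 and 5.6.3, define the competing event as the first treatment failure under section 5.4.4 without prior MMR, dated at the failure and coded 2. The section 5.4.4 list already includes discontinuation for any reason and notes that a reason of completed is not a premature stop, so no second definition is needed. In section 5.6.3, replace the reference to patients who dropped out with this event. The censoring rule in section 2.7.2 then applies only to patients with no MMR and no failure by cut-off, whose PCRs are all admissible, and the analysis agrees with section 2.1.1 and the primary estimand.

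The cost is one sentence, one event-code line and a rerun of one descriptive output. The failure date is already derived for TTF. Reporting, by arm, the number of patients whose code changes from 0 to 2 would show whether the point mattered in practice.
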